12.2.2 Analyses of Secondary Endpoints

Comparison of time to PSA progression will be performed using a two-sided log-rank test. Kaplan-Meier methods will be used to estimate medians for each treatment arm. Cox proportional-hazard models, including the same factors as above, will be used to estimate the hazard ratio and its 95% confidence interval (CI).

Adverse events (AEs) will be graded according to the NCI Common Terminology Criteria for Adverse Events (CTCAE) Version 4.03. All AEs reported from the first dose of study drug until 30 days after the last dose of study drug will be considered as treatment-emergent AEs and will be summarized by treatment arm. For each treatment arm, adverse event incidence rates will be summarized with frequency and percentage, with all patients treated in that treatment arm as the denominator, unless otherwise specified. In addition, AE incidence rates will also be summarized by severity and relationship to study drug. Treatment-related AEs are those judged by the Investigator to be at least possibly related to the study treatment. Adverse events with missing severity or relationship to study drug will be classified as severe and treatment-related, respectively.

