9.1.5 Attribution

A suspected adverse reaction means any adverse event for which there is reasonable possibility that the study drug caused the adverse event. For the purposes of IND safety reporting, “reasonable possibility” means there is evidence to suggest a causal relationship between the drug and the adverse event.

The Investigator will assign attribution of the possible association of the event with the study drug using the following definitions:

- **Unrelated to study drug:** The adverse event is *clearly not related* or is *doubtfully related* to the study drug
- **Related to study drug:** The adverse event *may be related*, is *likely related*, or is *clearly related* to the study drug

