9.3.1 SAE Reporting to the Sponsor-Investigator and Janssen

All participating sites will report SAEs to the Sponsor-Investigator within 24 hours of knowledge of the event. The Sponsor-Investigator will report to Janssen within 24 hours of being notified of the event, using MedWatch forms, as outlined below:

Procedures for Reporting Safety Data and Product Quality Complaints (PQCs) for Janssen Medicinal Products to Janssen

All adverse events and special situations, whether serious or non-serious, related or not related, following exposure to a Janssen medicinal product are to be documented by the investigator and recorded in the CRF and in the subject's source records. Investigators must record in the CRF their opinion concerning the relationship of the adverse event to a Janssen medicinal product.

All (serious and non-serious) adverse events reported for a Janssen medicinal product should be followed-up in accordance with clinical practice.

SAEs and Special Reporting Situations

All serious adverse events that have not resolved by the end of the study, or that have not resolved upon discontinuation of the subject's participation in the study, must be followed until any of the following occurs:

- The event resolves
- The event stabilizes
- The event returns to baseline, if a baseline value/status is available
- The event can be attributed to agents other than the study drug or to factors unrelated to study conduct
- It becomes unlikely that any additional information can be obtained (subject or health care practitioner refusal to provide additional information, lost to follow-up after demonstration of due diligence with follow-up efforts)

All participating sites will report all SAEs and special situations following exposure to a Janssen product under study to the Sponsor-Investigator within 24 hours of knowledge of the event, using MedWatch forms. UCSF and the Sponsor-Investigator will transmit all SAEs and special situations following exposure to a Janssen product under study using MedWatch form within 24-hours of becoming aware of the event(s).

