All follow-up information for serious adverse events that are not resolved at the end of the study or by the time of patient withdrawal must be reported by participating sites to the Sponsor-Investigator within 24 hours of knowledge of the event. SAE follow-up information will be reported directly to Janssen by the Sponsor-Investigator, within 24 hours becoming aware, using the MedWatch form. The Sponsor-Investigator will also notify the UCSF DSMC of any SAEs.

Reporting Deaths: Regardless of relationship to study drug, all deaths on study should be reported to Janssen through and including 30 days after the last dose of study. Deaths occurring after the safety follow-up period do not have to be reported as SAEs unless considered related to study drug. All study drug related deaths should be reported to the UCSF DSMC within 1 business day of becoming aware. All deaths will be reviewed by the UCSF DSMC.

All available clinical information relevant to the evaluation of a related SAE or special situation is required.

- For all SAEs, the Investigator is obligated to pursue and provide information to the Sponsor-Investigator and Janssen in accordance with the timeframes for reporting specified above. In addition, an Investigator may be requested to obtain specific additional follow-up information in an expedited fashion. This information may be more detailed than that captured on the AE CRF. In general, this will include a description of the adverse event in sufficient detail to allow for a complete medical assessment of the case and independent determination of possible causality.
- Information on other possible causes of the event, such as concomitant medications and illnesses must be provided. In the case of a patient death, a summary of available autopsy findings must be submitted as soon as possible to the Sponsor-Investigator or designated representative and Janssen.
- UCSF and the Sponsor-Investigator is responsible for ensuring that these cases are complete and if not are promptly followed-up. A safety report is not considered complete until all clinical details needed to interpret the case are received. Reporting of follow-up information should follow the same timeline as initial reports.

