All events should be followed to their resolution, until the Investigator assesses them as stable, irreversible, or until the patient is lost to follow-up, whichever comes first. Any SAEs occurring any time after the reporting period must be promptly reported if a causal relationship to apalutamide is suspected.

Copies of SAE Reporting to Regulatory Authorities to Janssen within 24 hours:

Copies of any and all relevant correspondences with regulatory authorities and ethics committees regarding any and all serious adverse events, irrespective of association with the Janssen Product under study, **are to be provided to Janssen within 24 hours of such report or correspondence being sent to applicable regulatory authorities.**

Product Quality Complaint (PQC) Handling:

A product quality compliant is defined as any suspicion of a product defect related to a potential quality issue during manufacturing, packaging, release testing, stability monitoring, dose preparation, storage or distribution of the product, or delivery system. Not all PQCs involve a subject. Lot and batch numbers are of high significance and need to be collected whenever available.

Examples of PQC include but not limited to:

- Functional Problem: e.g., altered delivery rate in a controlled release product
- Physical Defect: e.g. abnormal odor, broken or crushed tablets/capsules
- Potential Dosing Device Malfunction: e.g., autoinjector button not working, needle detaching from syringe
- Suspected Contamination
- Suspected Counterfeit

PQC Reporting:

A PQC may have an impact on the safety and efficacy of the product. Timely, accurate, and complete reporting and analysis of PQC information from studies are crucial for the protection of patients, investigators, and Janssen, and are mandated by regulatory agencies worldwide. Janssen has established procedures in conformity with regulatory requirements worldwide to ensure appropriate reporting of PQC information. Lot and/or Batch #s shall be

collected or any reports failure of expected pharmacological action (i.e., lack of effect). The product should be quarantined immediately and if possible, take a picture.

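### The planned safety summary follows the apalutamide clock and study-drug attribution, so a new late SBRT-related SAE or death has no place in it (minor)

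*Combined protocol and SAP*

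**What the plan says.** Sections 2.2 and 3.2.2 make the safety of apalutamide with SBRT a secondary objective and endpoint. The one planned adverse event analysis is in 12.2.2. It takes "All AEs reported from the first dose of study drug until 30 days after the last dose of study drug" as treatment-emergent, summarises these events by arm, and adds that "AE incidence rates will also be summarized by severity and relationship to study drug". It also states that "Treatment-related AEs are those judged by the Investigator to be at least possibly related to the study treatment".

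On attribution, 9.1.5 reads: "The Investigator will assign attribution of the possible association of the event with the study drug using the following definitions". The two categories that follow are related and unrelated to study drug. Appendix 6 (3.1), to which 9.2 refers the reader, uses a four-level scale of relationship to the investigational agents or a study procedure.

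On late reporting, 9.3.1 has two specific triggers: "Any SAEs occurring any time after the reporting period must be promptly reported if a causal relationship to apalutamide is suspected", and "Deaths occurring after the safety follow-up period do not have to be reported as SAEs unless considered related to study drug". The same section also says, with no end date, "All participating sites will report SAEs to the Sponsor-Investigator within 24 hours of knowledge of the event", and "The Sponsor-Investigator will also notify the UCSF DSMC of any SAEs". Appendix 6 (3.2) likewise sends all SAEs to the coordinating center and into OnCore, again with no stated end date.

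After treatment, 8.6 schedules PSA draws only, every 28 days until confirmed progression. Section 10 puts men who stop treatment without progression into the same follow-up.

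**The concern.** The arms differ only in SBRT, yet the safety window is set by the last apalutamide dose, whenever SBRT was given. An SBRT-related SAE or death that begins after the window, while the man is still on study, falls outside the treatment-emergent table, and section 12.2 has no other listing that would show it.

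Attribution adds to this. Section 4.3 stops therapy for unacceptable events related to apalutamide or SBRT, and 5.3.5 asks which study treatment was responsible for a delay. So investigators must judge SBRT causation, but 9.1.5 gives them nowhere to record it. The Appendix 6 scale gives one combined relationship, which does not separate drug from radiotherapy.

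At stake is completeness. The sponsor and the DSMC could know of a late SBRT-related death that the planned safety results on the tested treatment would not contain. Section 3.1 intends this trial to justify a phase 3 study of the same addition.

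**Working it through.** The plan states no figure on this point. Its one statistical figure, 84% power in 12.2.5, reproduces as 83.6% (one-sided Fisher's exact test at 0.10, 27 evaluable per arm, 25% against 2.5%) and is not affected.

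**Inputs**
- Apalutamide lasts 52 weeks (section 10): 52 x 7 = 364 days.
- The safety window ends 30 days after the last dose (12.2.2).
- SBRT starts within 90 days of apalutamide (5.6; Appendix 1, note 6). Section 8.3 mentions 60 days.
- First dose is 0 to 7 days after randomisation (4.5).
- The primary endpoint is at 18 months from randomisation (3.2.1).
- 30 men per arm, 10% inevaluable or dropped out (12.2.5).

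**Men who complete 52 weeks**

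The window closes on day 364 + 30 = 394 after first dose.

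| SBRT start | Days covered after SBRT start |
|---|---|
| day 0 | 394 - 0 = 394 |
| day 60 | 394 - 60 = 334 |
| day 90 | 394 - 90 = 304 |

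Month 18 is 18 x 30.44 = about 548 days from randomisation, so day 541 to 548 from first dose. The part outside the summary is 541 - 394 = 147 to 548 - 394 = 154 days. That is 147/28 = 5.25 to 154/28 = 5.5 intervals, or about five PSA draws. It is the most a man can have before month 18, because follow-up ends at progression or new therapy. For a man still free of progression at month 18, later follow-up is outside the summary too.

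**Men who stop apalutamide early without progression, SBRT started on day 90**

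Coverage after SBRT start = (stop day + 30) - 90. The stop days are illustrative.

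| Apalutamide stops | Days covered after SBRT start |
|---|---|
| day 90 | 120 - 90 = 30 |
| day 180 | 210 - 90 = 120 |
| day 270 | 300 - 90 = 210 |

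In the first row the window closes on day 120, which leaves 541 - 120 = 421 to 548 - 120 = 428 days to month 18.

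**How many men this could be**

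0.10 x 30 = 3 men in the SBRT arm. The 10% also covers withdrawals and losses to follow-up, so the group that stops early and stays in PSA follow-up should be smaller still if the assumption holds.

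**Reporting and analysis compared**

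The undated all-SAE wording in 9.3.1 and Appendix 6 (3.2) can bring a late SBRT event to the sponsor, the DSMC and OnCore. The notification of deaths related to a study procedure (9.3.3 and Appendix 6, 3.2) is limited to the treatment phase or 30 days after the last dose. None of these rules places a later event in the 12.2.2 summary.

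**The case against.** The strongest reply is that the window largely fits the stated endpoint, which concerns apalutamide with concurrent SBRT. Completers are covered for 10 months or more after SBRT start, and events that begin in the window are followed to resolution or stability (9.3.1, 9.3.2). This stands, and it makes the gap modest for most men.

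A second reply is that SBRT attribution is not absent. Appendix 6 (3.1) allows relationship to a study procedure, and the treatment-related sentence in 12.2.2 speaks of study treatment, which can include SBRT. This also stands. The defect is a mismatch: 9.1.5 and the 12.2.2 tabulation name study drug, the appendix combines agents and procedures, and neither separates the two treatments.

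A third reply is that late SAEs need not be lost as data. A reader might infer from the drug-specific triggers that a late SBRT-related SAE would go unreported. The documents do not support that. Those triggers sit in text largely about reporting to the drug manufacturer, and the undated clauses can be read to require the report. What remains on reporting is an ambiguity.

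None of the replies gives a new late event a place in the planned results.

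**Conclusion.** The point holds as a minor, cheap improvement. The planned safety results leave out new SBRT-related SAEs and deaths that begin more than 30 days after the last apalutamide dose, even while the man is on study. For completers this is about 147 to 154 days before month 18, after 304 to 394 days of coverage. The gap is larger only for the few men who stop apalutamide early without progression. The 30-day case requires the drug to stop on the day SBRT starts, at the 90-day limit.

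The day counts assume 52 full weeks of apalutamide and SBRT start between day 0 and day 90. The expected number of early stoppers rests on the plan's 10% assumption.

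A reader might go further and infer that safety is biased between arms, or that a known number of late toxicities will be missed. The documents give no late SBRT event rate, so neither can be shown. The primary test and its power are unaffected.

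**What to change.** 1. In 9.1.5, record relationship separately to apalutamide and to protocol SBRT, on a scale aligned with Appendix 6 (3.1). Have 12.2.2 tabulate both.
2. In 12.2.2, add a descriptive listing by arm of SAEs and deaths with onset after the 30-day window and before on-study follow-up ends (progression, new therapy or withdrawal). Show relationship to apalutamide and to protocol SBRT. Keep it apart from the treatment-emergent table and make no formal comparison, because before progression only the SBRT arm receives protocol SBRT.
3. In the late SAE and late death clauses of 9.3.1, extend the triggers for reporting to the Sponsor-Investigator and the DSMC to apalutamide or protocol SBRT. Leave the existing all-SAE wording as it is: replacing it with a relatedness condition would narrow reporting in an open-label trial.

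The word protocol matters, because the Study Design entry of the abstract allows SBRT in either arm after progression.

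The cost is one CRF field, one listing and possibly a few extra SAE forms, with no new visit or procedure. Capture stays passive: 8.6 schedules PSA only, so the listing will hold only the late events that sites learn of.

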12.2.3 Analysis of Exploratory Endpoints

The number and distribution of lesions detected on PSMA PET scan at baseline and at the time of PSA progression will be summarized using descriptive statistics for each treatment arm.

To determine the genomic factors associated with the development of oligometastatic disease, patient tumor biopsies will be compared to independent datasets of RNA/DNA sequencing from tumors obtained from patients with localized prostate cancer as well as those with more widespread castration-resistant prostate cancer. These analyses will be largely descriptive in nature.

Gene expression levels and genomic alterations (single nucleotide variants and/or copy number changes) in metastatic tumor biopsies and in germline DNA will be investigated for an association with efficacy outcomes using appropriate statistical methods (e.g. categorical or survival models), depending on the endpoints. Analyses may be performed within and between each treatment group. Other clinical covariates (such as baseline clinical disease characteristics and patient demographics) may also be included in the model. Association of biomarkers with clinical response or relevant time-to-event endpoints will also be explored in the overall population to identify “high-risk” biomarker profiles that are correlated with poor outcome.

Note: The italicized endpoints above were discontinued in Protocol v. 8.0. See Section 7.3 for additional information.

Whenever available, archival primary prostate cancer tissue for patients enrolled on the current study will be analyzed for gene expression patterns and compared to the patterns of gene expression observed in the baseline and progression tumor biopsies obtained at from an oligometastatic site of disease.

The number and site of oligometastatic sites of disease on baseline PSMA PET scan, as well as the PSMA avidity (SUVmax) for each lesion will be descriptively reported. Intra- and inter-lesional heterogeneity of uptake will be characterized using descriptive statistics. The association between patterns of uptake on baseline PSMA PET with outcomes on study will be investigated using appropriate statistical methods (e.g. categorical or survival models) as appropriate, within and across treatment groups.

12.2.4 Interim Analysis

No interim analysis will be performed, as the primary endpoint (PSA undetectable rate 6 months following completion of protocol treatment) will not be evaluable until after all patients have been accrued on study.

12.2.5 Determination of Sample Size

The sample size is based upon the primary endpoint of the study, the proportion of patients with an undetectable serum PSA (< 0.2 ng/mL) 6 months following completion of protocol therapy with apalutamide. Assuming a 10% inevaluable/drop-out rate per treatment arm, a sample size of 60 patients (30 patients/arm) provides 84% power to detect a difference in proportion of patients with undetectable PSA of 25% in the apalutamide + SBRT arm vs. 2.5 % in the apalutamide without SBRT treatment arm, with a unidirectional level of significance of 0.10 using Fisher's exact test.

13 STUDY MANAGEMENT

13.1 INVESTIGATOR RESPONSIBILITIES

The investigator is responsible for ensuring that the study is performed in accordance with current ICH guidelines on Good Clinical Practice (GCP), and applicable regulatory and country-specific requirements.

Good clinical practice is an international ethical and scientific quality standard for designing, conducting, recording, and reporting studies that involve the participation of human subjects. Compliance with this standard provides public assurance that the rights, safety, and well-being of the study subjects are protected, consistent with the principles that originated in the Declaration of Helsinki, and that the study data are credible.

To maintain confidentiality, all laboratory specimens, evaluation forms, reports and other records will be identified by a coded number. All study records will be kept in a locked file cabinet and code sheets linking a patient's name to a patient identification number will be stored separately in another locked file cabinet. Clinical information will not be released without written permission of the patient, except as necessary for monitoring by the FDA. The Investigator must also comply with all applicable privacy regulations (e.g., Health Insurance Portability and Accountability Act of 1996, EU Data Protection Directive 95/46/EC).

13.2 PRE-STUDY DOCUMENTATION

This study will be conducted in accordance with the ethical principles that have their origin in the Declaration of Helsinki as stated in 21 CFR §312.120(c)(4); consistent with GCP and all applicable regulatory requirements.

Before initiating this trial, the Investigator will have written and dated approval from the Institutional Review Board for the protocol, written informed consent form, subject recruitment materials, and any other written information to be provided to subjects before any protocol related procedures are performed on any subjects.

The clinical investigation will not begin until either FDA has determined that the study under the Investigational Drug Application (IND) is allowed to proceed or the Investigator has received a letter from FDA stating that the study is exempt from IND requirements.

The Investigator must comply with the applicable regulations in Title 21 of the Code of Federal Regulations (21 CFR §50, §54, and §312), GCP/ICH guidelines, and all applicable regulatory requirements. The IRB must comply with the regulations in 21 CFR §56 and applicable regulatory requirements.

13.3 INSTITUTIONAL REVIEW BOARD APPROVAL

The protocol, the proposed informed consent form, and all forms of participant information related to the study (e.g., advertisements used to recruit participants) will be reviewed and approved by the UCSF Institutional Review Board or the IRB of the participating site. For UCSF, prior to obtaining IRB approval, the protocol must be approved by the Helen Diller Family Comprehensive Cancer Center Site Committee and by the Protocol Review Committee (PRC). The initial protocol and all protocol amendments must be approved by each respective IRB prior to implementation.

13.4 INFORMED CONSENT

All participants must be provided a consent form describing the study with sufficient information for each participant to make an informed decision regarding their participation. Participants must sign the IRB-approved informed consent form prior to participation in any

study specific procedure. The participant must receive a copy of the signed and dated consent document. The original signed copy of the consent document must be retained in the medical record or research file.

